Once identified, patients will receive the following guideline-concordant content as part of the intervention: a) diet/lifestyle support, with counseling on hypocaloric diet and moderate-intensity exercise;⁵ b) NAFLD education;⁵ c) medication management, with proactive use of T2D medications known to be protective against NAFLD progression (pioglitazone, GLP-1RA, SGLT2i);^{5, 7, 16} and d) clinically-indicated liver testing and care based on guidelines.⁵ The content of this intervention will be delivered remotely via telehealth approaches. In order to ensure feasibility within the proposed KL2 timeline, we have limited the pilot duration to 3 months. This will allow time to observe change in liver enzymes, as well as HbA1c. Table 1

shows when intervention content will be delivered throughout the

Study population: We will enroll 10-15 Latinx/Hispanic and 10-15 Black patients with T2D and NAFLD, based on elevated ALT and exclusion of other liver diseases (e.g., viral hepatitis, alcohol abuse).

Research activity:

Detection of NAFLD in T2D: The Duke DEDUCE tool will be used to generate a report of potentially eligible Latinx and Black patients with an ICD code for T2D (E11.xx) and at least one ALT >40 IU/mL in males or > 31 IU/mL in females¹⁷ in the preceding 12 months. For this feasibility pilot, we will also restrict eligibility to patients who have a PCP or Endocrinologist in DUHS to facilitate communication regarding T2D medication changes during the study period. We anticipate >2,000 patient will meet our inclusion and exclusion criteria. A report will be exported from DEDUCE and I will review the charts of potentially eligible patients to exclude individuals with liver dysfunction likely due to an etiology other than NAFLD. We will not exclude patients with an ICD-10 code for NASH (K75.81), as long as they are not medically optimized (i.e. on pioglitazone and GLP-1RA), since these individuals serve to benefit from the intervention.

The first 50 patients who meet eligibility will be mailed a letter or sent a MyChart message with opt-out instructions. Patients who do not opt out will be contacted by phone and, if interested, they will sign an e-

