consent form via REDCap. In parallel to the above recruitment approach, we will also advertise this study in the community with the help of community partners that had assisted us in the design of the intervention, i.e., Latin-19 group and the AME Zion partnership. An IRB-approved flyer (with brief inclusion/exclusion criteria) will be created and placed in community spaces with the help of our community partners. Community members who are interested in the study, and who

Table 1: NAFLD-DM study visits and timing	Months			
	0	1	2	3
Enrollment, consent review (~20 min, remote visit)	x			
Surveys (~20-30 min, online or on phone)	x			x
NAFLD education (~30 min, remotely)	x			
Diet and lifestyle support (~30 min each, remotely)	x	x	x	
Medication changes (~20 min, remotely) *	o	o	o	o
If indicated, ordering tests and referrals *	o	o	o	o
Interviews (~30 min, remotely)				x

*Timing of med changes and ordering of tests/referrals will vary by participant.
x Visits that will occur for all participants.
o Visits that may or may not occur and are dependent upon individual needs.

are also part of DUHS, will be provided with a study contact number to let us know of their interest. We will use the EHR to determine their eligibility, and if eligible, consent will be obtained as above.

Baseline surveys will be conducted by phone or completed online via Duke REDCap. For participants completing surveys by phone, we will ensure that a copy of the survey is mailed or emailed in advance, in case participants prefer to review content in advance. We will survey: self-efficacy,¹⁸ and quality of life surveys¹⁹). The most recent BMI in the EHR will be used for the purpose of characterizing the participant population – if there is no BMI documented within 1 year of enrollment, we will count BMI data as missing. For HbA1c, if there is no documented HbA1c within 3 months of enrollment to the study, or ALT and ALT within 6 months of enrollment, we will order these tests to be completed at baseline.

Improving detection and evidence-based care of NAFLD in Latinx and Black patients with type 2 diabetes (NAFLD-DM): A pilot study

PI: [name]

Page 4 of 7

Version 2: May 31, 2024

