Evidence-based care of NAFLD in T2D: Intervention content will include: 1) NAFLD education; 2) diet/lifestyle support; 3) T2D medication management; and 4) clinically-indicated liver testing and care. [name] (PI) and the Clinical Research Coordinator (CRC) will deliver NAFLD education and diet/lifestyle support content. [name] (PI) will conduct medication management, which will involve review of glycemic trends, assessment of hypoglycemia and adjustment of the T2D regimen to accommodate initiation of pioglitazone, GLP-1RA and/or SGLT2i. The order in which these medications are considered will depend on clinical judgement, patient preference and cost, but GLP-1RA will be prioritized as appropriate, since this class has potent weight loss effects.¹⁶ Also, at baseline (and as indicated throughout the study), [name] (PI) will review clinical data and order clinically-indicated liver testing based on guidelines. Surveys and clinical evaluation will be repeated at study conclusion. A treatment acceptability measure (TAP)²⁰ will be administered at conclusion to gauge intervention acceptability. A detailed summary of data collection and outcome measures can be seen in Table 3.

Table 3: Detailed summary of data collection and outcomes	Method	Timing
Primary outcomes		
Feasibility		
System-level NAFLD detection	Patients who met criteria for NAFLD after chart review / total number of potentially-eligible patients based on our EHR criteria	3 months
Recruitment rate*	Patients eligible and sent letter or MyChart message / Patients enrolled	3 months
Retention rate	Patients enrolled / Patients completed study	3 months
Visit completion rate	Total study visits completed / total study visits scheduled	3 months
Acceptability		
	TAP measure ²⁰	3 months
	Qualitative interviews	3 months
Secondary outcomes of interest		
Medication changes made during the study	Study visit notes in EHR	0, 3 months
Proportion of patients in whom clinically-indicated tests were ordered (e.g. labs, referral, imaging).	Study visit notes in HER	0, 3 months
Psychosocial constructs Self-efficacy Autonomy support Quality of life	6-item SEMCD ²¹ HCCQ Diabetes ¹⁸ SF-12 ¹⁹	0,3 months
Descriptive data to characterize population		
Social and demographic Age, sex, race/ethnicity, marital status, education, employment, tobacco use, alcohol use, SDOH screen (food insecurity, housing instability, lack of transportation)	Self-reported surveys	0 months
Health literacy/numeracy	NVS	0 months

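### No contact fixed for every participant is stated to ask about harms, and neither Table 3 nor the SAP lists hypoglycemia, side effects or reasons for stopping a drug

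*Protocol*

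**What the plan says.** **Treatment.** Under Intervention content and design, the Protocol commits to "proactive use of T2D medications known to be protective against NAFLD progression", naming pioglitazone, GLP-1RA and SGLT2i. These come with "counseling on hypocaloric diet and moderate-intensity exercise", and everything is delivered remotely.

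**Clinical cover.** Under Evidence-based care of NAFLD in T2D, the investigator runs medication management, which includes checking for hypoglycemia. The investigator also reviews clinical data at baseline and later when indicated. A clinical evaluation is repeated at the end, with no content given. Eligibility is restricted to "patients who have a PCP or Endocrinologist in DUHS to facilitate communication regarding T2D medication changes during the study period".

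**Contacts.** Table 1 has two kinds. Those marked x are "Visits that will occur for all participants"; those marked o are "Visits that may or may not occur and are dependent upon individual needs". The medication-change row is o at every month from 0 to 3.

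**Measures.** Table 3 takes medication changes from study visit notes. The SAP's secondary outcomes are HbA1c, ALT and three survey measures.

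**The concern.** A study that starts glucose-lowering drugs and advises eating less would be expected to learn how often participants had hypoglycemia, felt unwell on a drug, or gave it up. Here the only harm enquiry described sits within medication management, which has no contact fixed for all, and its result feeds no listed measure. A blank in the notes could then mean that nothing happened or that nobody asked. The SAP wants the pilot to inform later work, and whether people tolerate and stay on the drugs bears directly on that. Detection is also at stake: a participant who stops a drug alone between contacts need not come to the investigator's attention through any contact described.

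**Working it through.** **Step 1. Contacts after month 0 (Protocol, Tables 1 and 3, Evidence-based care, Participant interviews).**

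| Contact | Fixed for all? | Described content | Harm question stated? |
|---|---|---|---|
| Diet/lifestyle, months 1 and 2 | Yes | Diet and exercise support | No |
| Survey, month 3 | Yes | Self-efficacy, autonomy support, quality of life | No |
| TAP, at conclusion | Given at conclusion | Acceptability; items not reproduced | Cannot be told |
| Interview, month 3 | Yes | Mainly acceptability and feedback on content | No |
| Closing clinical evaluation | Not a Table 1 row | Not described | Cannot be told |
| Medication-change contacts, months 0-3 | No | Part of investigator-led medication management | Hypoglycemia, as clinical care |

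**Step 2. Measures.** Table 3 can show who started or stopped a drug, but has no item for the reason, for side effects or for hypoglycemia. Its adherence questionnaire is given at month 0 only. The SAP lists no harm.

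**Step 3. Scale.** The plan has no figure to reproduce. The only inputs from the documents are enrolled totals: 10-15 per group, so 20 to 30 (Protocol, Study population), and 15 + 15 = 30 (SAP). Event rates, shares asked, numbers starting a drug and event counts below are assumptions.

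*(a) Uneven asking.* The chance of recording at least one event is 1 - (1 - p)^n. With p = 10%:
- All asked: 1 - 0.9^20 = 87.8%; 1 - 0.9^30 = 95.8%.
- Half asked: 1 - 0.9^10 = 65.1%; 1 - 0.9^15 = 79.4%.

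This assumes equal risk in those asked and not asked. Drug starters are the likelier to be asked, so for drug-related harm the loss may be smaller.

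*(b) What zero events would mean.* The exact two-sided 95% upper limit is 1 - 0.025^(1/n).
- All asked: 11.6% at n = 30, 16.8% at n = 20.
- Starters only, assuming 15, 10 or 5: 21.8%, 30.8%, 52.2%.

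*(c) Denominator.* If three starters report hypoglycemia and no one else does, Clopper-Pearson 95% intervals are:
- 3/15 = 20% (4.3% to 48.1%) among starters.
- 3/30 = 10% (2.1% to 26.5%) among all asked.

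*(d) Time window.* A past-month question at month 0 covers one month; a figure for ever reporting over months 1-3 covers three. With no true change and independent months:
- Monthly risk 10%: 1 - 0.9^3 = 27.1% against 10%.
- Monthly risk 5%: 1 - 0.95^3 = 14.3% against 5%.

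That comparison would show apparent harm by construction, so each month must be reported on its own.

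**The case against.** The strongest reply is that cover is wider than Table 1 suggests. Medication management is listed among the content that patients receive, and it includes a hypoglycemia check. The o row concerns medication changes, so it shows that a change visit is conditional, not that the check is. The closing evaluation or the TAP might ask about side effects. Stops, and any reasons noted, could be abstracted from visit notes. The treatment is described as guideline-concordant, and a pilot of 20 to 30 people yields wide intervals.

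Much of this stands. A reader might infer that hypoglycemia is never assessed, that someone who starts a drug goes unchecked, or that unrecorded harms are lost for good. The documents support none of these: the investigator's check is written into the plan, marking medication visits by need is reasonable care, and notes may preserve part of the information.

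It does not close the gap. The check is tied to no fixed contact and goes to no measure. The closing evaluation has no stated content. Notes written as needed do not show how many people were asked. The wide intervals argue against elaborate analysis, not against asking everyone the same questions.

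**Conclusion.** The point holds as a gap in uniform collection and reporting of harms, not as evidence that the study is unsafe. It should be fixed, and it changes no feasibility or acceptability criterion. Confidence is medium, because the closing evaluation and the TAP could cover part of it. The finding is limited to Table 1, Table 3, the protocol text on care and interviews, and the SAP. Safety reporting described elsewhere cannot be seen, and would not by itself give a count among people who were all asked.

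The size cannot be derived from the documents. The calculations illustrate the effect of uneven asking, the need for two denominators and the trap in unequal time windows; no study decision rests on them.

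**What to change.** **Ask.** At the month 1 and 2 diet/lifestyle contacts and the live month 3 interview, put the same short questions to every participant: hypoglycemia in the past month, other side effects, and any study-started drug stopped and why. Ask the hypoglycemia question at month 0 as well. Since the investigator "and the Clinical Research Coordinator (CRC) will deliver NAFLD education and diet/lifestyle support content", the script needs a route for passing positive answers to the investigator when the coordinator leads. The live interview is better than the online survey at month 3, because survey answers would need someone to review them promptly.

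**Record and report.** Add one secondary row to Table 3 and a short SAP statement giving simple counts and percentages:
- Past-month hypoglycemia separately at months 0, 1, 2 and 3, each with the number asked. Never set a cumulative months 1-3 figure against month 0.
- Other side effects, among all asked and among those who started a study drug.
- Stops of a study-started drug, with reasons, among starters only.

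Confidence intervals are optional and descriptive.

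**Cost.** A few minutes of participant and staff time at existing contacts, a short script, and a minor protocol amendment. No new visits or staff.

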Medication adherence	VMNQ ²²	0 months
Clinical Baseline knowledge of NAFLD, years with diabetes, medical history, medication use	Self-reported surveys	0 months

Improving detection and evidence-based care of NAFLD in Latinx and Black patients with type 2 diabetes (NAFLD-DM): A pilot study

PI: [name]

Page 5 of 7

Version 2: May 31, 2024

Labs: HbA1c, AST, ALT	Use from EHR if collected within 3 months of baseline visit. Otherwise, research labs collected in DUHS at specified time points.	0 months
Biomedical Height, weight, BMI	From EHR (last recorded values)	0 months

*We will also track the number of participants who expressed interest in the study based on our recruitment flyer, and examine the recruitment rate via this approach (i.e., patients who expressed interest / patients enrolled. **Abbreviations:** TAP=Treatment Acceptability & Preferences; SDOH=social determinates of health; NAFLD=nonalcoholic fatty liver disease; BMI=body mass index; HER=electronic health record; SEMCD=Self-efficacy to Manage Chronic Disease Scale; VMNQ=Voils Medication Non-Adherence Questionnaire; NVS=Newest Vital Sign; HCCQ=Healthcare Climate Questionnaire.

Participant interviews: At study conclusion, individual 30-minute virtual interviews will be conducted with all study participants. The primary purpose will be to assess intervention acceptability and to gain specific feedback about intervention content. Thematic saturation is expected by 12 interviews.²²

Quantitative analysis: Intervention feasibility will be evaluated by examining recruitment rates, retention rates, and study visit completion rates. For the TAP measure, mean score and standard deviation will be calculated. This feasibility pilot will not be powered to examine changes in clinical measures (e.g., HbA1c, ALT).

Qualitative analysis: All interviews will be digitally recorded and transcribed. Transcripts will be analyzed with direct content analysis.²³

Improving detection and evidence-based care of NAFLD in Latinx and Black patients with type 2 diabetes (NAFLD-DM): A pilot study

PI: [name]

Page 6 of 7

Version 2: May 31, 2024

References

2. Diabetes Mellitus. *Federal Practitioner*. 2017;

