Official Title: Improving Detection and Evidence-based Care of NAFLD in Latinx and Black Patients With Type 2 Diabetes (NAFLD-DM): A Pilot Study

NCT: NCT05844137

IRB Document Date: 5/31/2024

Statistical Design and Power

V: May 31,2024

We expect to enroll 15 participants who self-identify as Black or African American (AA), and 15 participants who self-identify as Hispanic/Latinx.

Our quantitative primary outcomes will be feasibility and acceptability, as below:

| | |
|---|--|
| Feasibility of system-level NAFLD detection approach | Patients who met criteria for NAFLD after chart review / total number of potentially-eligible patients based on our EHR criteria. We will deem this approach feasible if detection rates are >70%. |
| Feasibility of patient-level management | We will assess recruitment rates, retention rates and study visit completion rates. We will consider our management approach to be feasible if we can recruit at least 10 Black/AA patients and 10 Hispanic/Latinx patients over 12 weeks (3 months) |
| Acceptability of intervention by participants | We will calculate the mean and standard deviation of the Treatment Acceptability and Preferences (TAP) measure at 3 months; a score >3 will be deemed acceptable. |

Secondary outcomes: Patient-level outcomes will be examined at 12 weeks (3 months), and these include: hemoglobin A1c, alanine aminotransferase level (ALT), and survey measures (i.e., self-efficacy, perceived autonomy support and quality of life). Effect size of the pre-post difference and 95% confidence intervals will be calculated.

This pilot study will not have enough statistical power to establish effectiveness of the intervention for these secondary outcomes. Results of an intervention to improve NAFLD detection and management in Black and/or Hispanic/Latinx persons with T2D has not been previously reported. Therefore, the primary goal of this pilot study is to generate evidence in this area to estimate effect sizes and show feasibility of the intervention to guide future work.

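### A chart HbA1c up to 3 months old can serve as baseline with no check for regimen changes since, so the uncontrolled pre-post effect may include change that preceded the intervention

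*Protocol*

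**What the plan says.** **Baseline value.** In the Protocol's Research activity section, the paragraph on baseline surveys has a new HbA1c ordered "if there is no documented HbA1c within 3 months of enrollment to the study". The Labs row of Table 3 gives the same window: "Use from EHR if collected within 3 months of baseline visit", and a research lab otherwise. A recent chart value therefore takes the place of a fresh draw.

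**Regimen.** No passage asks whether glucose-lowering treatment was unchanged between the chart sample and enrolment. The pilot will "restrict eligibility to patients who have a PCP or Endocrinologist in DUHS", and the stated reason is communication about medication changes during the study. Table 3 counts medication changes only within the study. Baseline medication use is self-reported at month 0 and is not tied to the lab date. The only eligibility limit that concerns treatment is for patients with a NASH code who are already medically optimized.

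**Analysis.** The SAP's paragraph on secondary outcomes says: "Patient-level outcomes will be examined at 12 weeks (3 months), and these include: hemoglobin A1c, alanine aminotransferase level (ALT), and survey measures". It continues: "Effect size of the pre-post difference and 95% confidence intervals will be calculated". No comparator is described. The SAP gives the pilot's main goal as generating evidence "to estimate effect sizes and show feasibility of the intervention to guide future work".

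**Status of HbA1c in the protocol.** Table 3 lists it under descriptive data, at 0 months only. The text on evidence-based care says that clinical evaluation is done again at the end of the study, but does not name HbA1c.

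**The concern.** The look-back window is as long as the follow-up. The protocol explains the follow-up as follows: "we have limited the pilot duration to 3 months", and then "This will allow time to observe change in liver enzymes, as well as HbA1c". If 3 months is long enough for the intervention to move HbA1c, it is also long enough for a treatment change made before enrolment to move it.

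Every participant has a clinician in the health system who can change treatment. Suppose that clinician adds a glucose-lowering drug after the chart sample and the patient then enrols. The chart value precedes the drug and the month-3 value follows it. A pre-post difference without a control arm counts the whole change as the study's. At stake is the HbA1c effect size that the SAP wants to hand to future work. The lack of power that both documents admit is a matter of precision; this is a matter of bias, which more participants would not remove.

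**Working it through.** **1. Figure to reproduce.** There is none. The documents give no SD, no expected HbA1c change and no share of participants with a recent regimen change. What follows is an illustration under assumed inputs.

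**2. Interval between samples.** Look-back up to 3 months + follow-up 3 months = up to 6 months, so at most 3/6 = one half precedes the intervention. This is the extreme. A participant with no recent chart value is tested at baseline, and the interval is then about 3 months.

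**3. Bias in the mean change.** Bias = f × d. Here f is the share of participants intensified around or after the chart sample and before enrolment, and d is the mean HbA1c fall from that change that appears after the chart sample. Assumed: f = 10–30%, d = 0.5–1.0 points.

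| f | d = 0.5 | d = 1.0 |
|---|---|---|
| 0% | 0 | 0 |
| 10% | 0.05 | 0.10 |
| 20% | 0.10 | 0.20 |
| 30% | 0.15 | 0.30 |

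With an assumed SD of change of 1.0–1.5 points, the standardised effect size shifts by 0.05/1.5 = 0.03 to 0.30/1.0 = 0.30. For de-intensification the sign reverses.

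**4. Against the planned precision.** Half-width of the 95% interval = t(0.975, n−1) × SD/√n. The protocol plans 10–15 per group, so n = 20 to 30; the SAP expects 15 + 15 = 30.

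- n = 20: 2.093 × 1.0/4.472 = 0.47; with SD 1.5, 0.70.
- n = 30: 2.045 × 1.0/5.477 = 0.37; with SD 1.5, 0.56.

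The largest assumed bias, 0.30, is below the smallest of these, 0.37.

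**5. What the interval misses.** True coverage of the nominal 95% interval, from the noncentral t distribution with noncentrality bias × √n/SD:

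| n | SD | bias 0.05 | 0.10 | 0.20 | 0.30 |
|---|---|---|---|---|---|
| 20 | 1.0 | 94.5% | 92.9% | 86.4% | 75.3% |
| 20 | 1.5 | 94.8% | 94.1% | 91.2% | 86.4% |
| 30 | 1.0 | 94.2% | 91.7% | 81.5% | 64.5% |
| 30 | 1.5 | 94.6% | 93.6% | 89.1% | 81.5% |

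Coverage is close to nominal at the low end and clearly short only at the top of the assumed range.

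**6. What a fresh draw would remove.** If a fraction p of d has appeared by enrolment, a new baseline value leaves a bias of f × d × (1 − p). It removes everything if p = 1 and nothing if p = 0, so a drug started just before enrolment would still contribute.

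**The case against.** The strongest case on the other side is that the documents show only a possibility, and one confined to a side outcome.

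- **Frequency.** A reader might infer that usual-care changes are in fact being credited to the intervention, because a routine HbA1c tends to prompt intensification. The documents do not say so and give no rate. HbA1c is not an entry criterion; entry rests on a T2D code and a raised ALT, so participants are not selected for a recent high HbA1c. The protocol's background also says that the T2D drugs protective against NAFLD progression are much underused in high-risk patients. That gives no support to frequent recent intensification, though it does not rule out other changes. This objection stands: the share is unknown and may be zero.
- **Direction.** A reader might infer that the bias always favours the intervention. It does not, because stopping or reducing a drug before enrolment would work the other way. This also stands.
- **Separability.** A reader might infer that the effect could never be disentangled. But chart labs come from the EHR, medication use is collected at baseline, and the investigator reviews clinical data then. A later sensitivity analysis looks possible. It is not planned, however, and the review of clinical data serves care, not the validity of the baseline.
- **Importance.** Feasibility and acceptability are the primary outcomes and are untouched. Both documents disclaim power for clinical measures. This limits the weight of the point but does not answer it, since the SAP still wants effect sizes to plan from.
- **Root cause.** The deeper limitation is the uncontrolled design, and a fresh draw only partly helps. That is true, and the fix should say so.
- **Protocol against SAP.** On Table 3 alone there is no HbA1c change to bias; the issue arises from the SAP's analysis. This is a conflict to reconcile. It does not make the baseline rule sound for the SAP's purpose.

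**Conclusion.** The point holds as a minor one. Followed as written, the baseline rule lets the reported HbA1c change include the effect of treatment changes made before enrolment, and nothing planned would detect this. The mechanism follows from the text; the size does not. The range of 0.05–0.30 points rests wholly on the assumed 10–30% and 0.5–1.0 points, with zero as the lower limit if no regimen changed and the opposite sign under de-intensification. At assumed SDs of 1.0–1.5, that range is smaller than the interval's half-width but is not reflected in it.

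The documents do not support a reading in which the pilot's conclusions are compromised. One unpowered secondary outcome is affected, and the change to the plan is optional.

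**What to change.** 1. Record the date of the HbA1c used as baseline, and any change in the glucose-lowering regimen from that date (the sampling day included) to enrolment.
2. Where there was a change, draw the baseline research HbA1c through the route that Table 3 already provides. This is a measurement rule and alters no treatment.
3. In the SAP, report the pre-post HbA1c effect size and interval with and without these participants.
4. State that delayed effects of earlier regimen changes and regression to the mean remain in the estimate, because there is no control arm.
5. Reconcile Table 3 (HbA1c as descriptive data at 0 months) with the SAP (secondary outcome at 12 weeks).

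The cost is a sentence or so in the protocol text, Table 3 and the SAP, and a few extra draws among 20–30 participants. The HbA1c estimate may come out less favourable.

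### The TAP and the interviews are scheduled only at month 3, with no procedure for people who stop early, so the acceptability verdict will probably rest mainly on completers

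*Protocol*

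**What the plan says.** The protocol lists acceptability as a primary outcome in Table 3, with two measures, the TAP and qualitative interviews, both timed at 3 months. The section on evidence-based care of NAFLD in T2D says the TAP "will be administered at conclusion to gauge intervention acceptability". The Participant interviews section says: "At study conclusion, individual 30-minute virtual interviews will be conducted with all study participants". Table 1 marks interviews at month 3 only, and its legend defines the mark as "x Visits that will occur for all participants". Table 1 does not name the TAP.

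On analysis, the protocol says "For the TAP measure, mean score and standard deviation will be calculated". The SAP says "We will calculate the mean and standard deviation of the Treatment Acceptability and Preferences (TAP) measure at 3 months" and adds that "a score >3 will be deemed acceptable". The natural reading is that the mean is compared with 3. No test, alpha or confidence interval goes with that threshold. The SAP does not mention the interviews.

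Retention and visit completion are primary feasibility measures. The SAP's only pass rule for patient-level management, however, is recruiting 10 or more people in each of the two groups within 12 weeks.

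Neither document provides for a TAP or interview at early stopping, a denominator for the TAP mean, a rule for missing scores, or a limit of the claim to completers.

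**The concern.** Because retention is itself an outcome, the plan foresees that some people may leave. Someone who stops after month 0 or month 1 has had some of the intervention and may have a view of it, but the plan describes no step that would record that view. If some leave because they do not like the intervention, their low ratings go unrecorded and the mean is taken over those more content to stay. The pass/fail verdict could then look better as dissatisfied people leave.

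Nothing else in the plan would register this as a failure. The patient-level feasibility rule depends on recruitment alone, and retention has no cut-off. The interviews share the month-3 timing, so they do not fill the gap. Saturation is anticipated after 12 interviews, a count that completers alone could reach. For a pilot meant to inform later work, the reasons people stopped are among the most useful things it could learn.

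**Working it through.** The plan gives no figure to reproduce: it states no expected dropout, TAP mean, SD or score range. What follows is sensitivity arithmetic.

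**Inputs from the documents.** Threshold 3 (SAP). Enrolment N of 20 to 30 (protocol, 10–15 per group) or 30 (SAP, 15 + 15).

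**Assumptions, not in the documents.** Completer mean m, proportion leaving d, and the mean x that leavers would have given.

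**Step 1: the leaver mean at which the all-enrolled mean equals 3.** The all-enrolled mean is (1 − d)·m + d·x. Setting it to 3 gives x = (3 − m(1 − d))/d. For m = 3.3 and d = 0.2, x = (3 − 2.64)/0.2 = 1.8. The same formula over a range of inputs gives:

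| Completer mean m | d = 10% | d = 20% | d = 30% | d = 40% |
|---|---|---|---|---|
| 3.1 | 2.10 | 2.60 | 2.77 | 2.85 |
| 3.3 | 0.30 | 1.80 | 2.30 | 2.55 |
| 3.5 | −1.50 | 1.00 | 1.83 | 2.25 |
| 3.8 | −4.20 | −0.20 | 1.13 | 1.80 |

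The verdict reverses only if leavers would average the tabulated value or less. Negative entries mean no reversal is possible on any scale without negative scores.

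**Step 2: worked cases with N = 30 and m = 3.3.** The month-3 mean passes in each case.

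- 6 leavers at 2.0: (24 × 3.3 + 6 × 2.0)/30 = 91.2/30 = 3.04, still above 3.
- 6 leavers at 1.0: (79.2 + 6)/30 = 85.2/30 = 2.84, below 3.
- 8 leavers at 2.0: (22 × 3.3 + 8 × 2.0)/30 = 88.6/30 = 2.95, below 3.

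**Step 3: the fewest leavers that bring the all-enrolled mean to 3 or below.** This is the smallest whole k with (N − k)·m + k·x ≤ 3N, that is, k ≥ N(m − 3)/(m − x). For N = 30, m = 3.3 and x = 1, k ≥ 9/2.3 = 3.9, so 4.

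| m | N = 30, x = 1 | N = 30, x = 2 | N = 20, x = 1 | N = 20, x = 2 |
|---|---|---|---|---|
| 3.1 | 2 | 3 | 1 | 2 |
| 3.3 | 4 | 7 | 3 | 5 |
| 3.5 | 6 | 10 | 4 | 7 |

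A completer mean close to 3 can be reversed by a handful of people. A mean well above 3, with few leavers, cannot.

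**The case against.** A reader might infer that leavers are excluded and cannot affect the mean. The documents do not say so. Interviews are planned with every participant, the month-3 survey and interview contacts are marked as occurring for everyone, and both are done remotely. Nothing limits the TAP to completers or bars contact with someone who has stopped. This stands in part: the text states intended coverage, but gives no procedure for reaching people who have left.

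A reader might also infer that the mean is biased upward. That requires leavers to rate the intervention lower. The documents give no reasons for leaving, and moving house, work or illness would not imply dislike. The direction is plausible but not established.

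Retention and visit completion are reported as primary outcomes next to the TAP, so a mean flattered by departures would appear beside poor retention. That is a real safeguard, but with no cut-off it discloses the problem without changing the verdict.

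The illustration also depends on its inputs. A completer mean of 3.3 lies close to the threshold. At 3.5 with 10% dropout, no non-negative leaver mean could reverse the result.

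Finally, an early-stop rating concerns only part of a three-month programme, so pooling it into the main mean would change what is measured. That objection is sound, and the fix keeps the two apart.

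**Conclusion.** The point holds as a weakness in how a primary outcome is collected and judged. Followed as written, the plan will probably give an acceptability verdict drawn mainly from completers, and no stated criterion would catch the effect of departures. The verdict may be too favourable, on the condition that leavers would have rated lower.

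The size cannot be fixed from the documents. With the assumed completer mean of 3.3, reversal needs a leaver mean of 1.8 or less at 20% dropout, but 0.3 or less at 10%. A changed verdict is therefore possible but not shown to be likely. Nor is this a faulty hypothesis test, since the threshold is descriptive. The study remains sound as a pilot; the change is worth making because the outcome is primary and the remedy is cheap.

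**What to change.** In Table 3 and the SAP, set the TAP timing to *3 months, or when a participant stops*. Offer it by the REDCap or phone route already used for surveys, with a voluntary interview. In the SAP:

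- Report the month-3 mean and the early-stop scores separately.
- Give the mean over all participants with any TAP as a sensitivity analysis for the verdict against 3.
- State the number with a TAP out of the number enrolled.
- Report the mean that those without a TAP would need for the overall mean to fall to 3. With n scores averaging m out of N enrolled, this is (3N − n·m)/(N − n).
- If only month-3 scores are available, word the conclusion *acceptable among completers*.

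The cost is a short wording change and a few extra contacts. Some leavers will not respond, and early-stop ratings will reflect only the part of the programme those people received.
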